8.1. Efficacy Assessments

Assessment of disease response and progression status in all subjects will be evaluated by the Investigator using 2007 IWG criteria ([Cheson 2007](#)) and 2014 Lugano criteria ([Cheson 2014](#)). Response and progression will be evaluated using the following procedures, as indicated in the SoA ([Table 1](#)).

- Focused physical examination (PE) (including assessment of liver and spleen and review of disease-related constitutional symptoms) (see Section [8.2.1.2](#))
- Imaging scans of chest, abdomen, and pelvis (see Section [8.1.1](#))
- Bone marrow biopsy/aspirate (see Section [8.1.2](#))

These evaluations will be done until progressive disease (PD) is documented, other anticancer therapy is initiated, or death occurs. For subjects who discontinue study intervention for reasons other than radiologic disease progression, response assessments will be performed during long-term follow-up (Section [8.1.4](#)).

8.1.1. Imaging Scans

All subjects require CT or ¹⁸Fluoro-2-deoxy-d-glucose (FDG) positron emission tomography (PET)-CT (PET-CT) scans of the chest, abdomen, and pelvis. Magnetic resonance imaging (MRI) may be used instead of CT scans if CT cannot be done, but the same method must be used

throughout the study. Other scans may be performed (e.g., neck/head) if clinically indicated or if the area is a site of known disease. Any new abnormal findings outside disease measurements should be captured as an AE.

8.1.2. Bone Marrow Biopsy/Aspirate

If a bone marrow/aspirate is performed within 60 days before C1D1 as part of standard of care, the pathology report will be provided to the Sponsor. If a radiologic CR according to 2007 revised IWG criteria ([Cheson 2007](#)) is observed during the course of the study, then a bone marrow biopsy should be done to confirm a CR. The pathology report will be provided to the Sponsor.

8.1.3. Investigator Assessment of Response and Progression Status

Assessment of response and progression status will be evaluated by the Investigator at each scheduled disease response assessment as outlined in the SoA ([Table 1](#)). Assessment of response and progression status in all subjects will be evaluated using the definitions from the 2007 revised IWG criteria ([Cheson 2007](#)) for clinical decision-making and assessment of response. Secondarily, response will also be assessed using the 2014 Lugano criteria ([Cheson 2014](#)). Please see Section [10.1](#) for detailed descriptions of these response criteria.

8.2. Safety Assessments

Planned time points for all safety assessments are provided in the SoA ([Table 1](#)). Additional visits may be conducted as necessary for any abnormal findings that require medical follow-up.

8.2.1. Physical Examinations and Vital Signs

8.2.1.1. Full Physical Examination

The full PE will include assessment of liver/spleen size, clinical assessment of tumor masses (if evaluable by PE), review of disease-related constitutional symptoms (B symptoms: symptoms of fever [i.e., temperature $> 38^{\circ}\text{C}/100.4^{\circ}\text{F}$] without evidence of infection, weight loss, and drenching night sweats without evidence of infection), neurologic exam, height, and weight.

Any pre-existing PE abnormality deemed clinically significant by the Investigator during Screening will be reported as medical history. Any PE abnormality that emerges or has worsened after signing of the ICF and that is assessed as clinically significant by the Investigator will be reported as an AE.

8.2.1.2. Focused Physical Examination

Each focused PE is to include assessment of liver and spleen size, clinical assessment of tumor masses and evaluation for the presence of disease-related constitutional symptoms (B symptoms: symptoms of fever [i.e., temperature $> 38^{\circ}\text{C}/100.4^{\circ}\text{F}$] without evidence of infection, weight loss, and drenching night sweats without evidence of infection).

Results from the focused PEs and assessments of ECOG performance status (Section [8.4.1](#)) will be used for assessment of disease response and safety. Additionally, any new or ongoing abnormal findings will be assessed. Any new clinically significant abnormality from baseline should be recorded as an AE.

8.2.1.3. Vital Signs

Vital signs will be measured in a semi-supine position after 5 minutes rest and will include temperature, systolic and diastolic blood pressure, pulse rate, and respiratory rate.

8.2.2. Electrocardiogram and Echocardiogram/Multi-gated Acquisition Scan

At Screening, a standard 12-lead electrocardiogram (ECG) will be conducted following an approximate 10-minute rest period. QTc measurements (as measured by triplicate readings) will use the Fridericia's correction method (QTcF).

To measure left ventricular ejection fraction (LVEF), an echocardiogram (ECHO) or multi-gated acquisition (MUGA) scan will be administered at the Screening Visit.

Additional ECGs and ECHO/MUGA scans may be performed as clinically indicated per Investigator's judgment.

8.2.3. Concomitant Medication and Procedures

Concomitant medications and procedures will be assessed and recorded in the CRF during Screening (including those occurring within 30 days prior to randomization) and at each visit.

8.2.4. Clinical Safety Laboratory Assessments

- See [Table 18](#) for the list of clinical laboratory tests to be performed and the SoA ([Table 1](#)) for the timing and frequency.
- The Investigator must review the laboratory report, document this review, and record any clinically relevant changes occurring during the study in the AE section of the CRF. The laboratory reports must be filed with the source documents. Clinically significant abnormal laboratory findings are those which are not associated with the underlying disease, unless judged by the Investigator to be more severe than expected for the subject's condition.
- All laboratory tests with values considered clinically significantly abnormal during participation in the study or within 30 days after the last dose of study intervention should be repeated until the values return to normal or baseline or are no longer considered clinically significant by the Investigator or the Medical Monitor.
 - If such values do not return to normal/baseline within a period of time judged reasonable by the Investigator, the etiology should be identified, and the Sponsor notified.
 - All protocol-required laboratory assessments, as defined in [Table 18](#), must be conducted in accordance with the Laboratory Manual and the SoA ([Table 1](#)).
 - If laboratory values from non-protocol-specified laboratory assessments performed at the institution's local laboratory require a change in subject management or are considered clinically significant by the Investigator (e.g., SAE or AE or dose modification), then the results must be recorded in the CRF.

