2.3. Benefit/Risk Assessment

2.3.1. Risk Assessment

As of 19 July 2018, in 588 subjects treated with duvelisib monotherapy in hematologic malignancy studies (see Section 6.3.4.1.2 in the IB), the most frequent treatment-emergent adverse events (TEAEs) ($\geq 20\%$ of subjects) reported were diarrhea/colitis (49.0%), neutropenia (34.7%), rash (34.7%), fatigue (33.2%), pyrexia (30.3%), cough (26.7%), nausea (26.0%), transaminase elevation (22.8%), musculoskeletal pain (22.6%), anemia (22.4%), upper respiratory tract infection (22.3%), and pneumonia (21.6%). The most frequently reported TEAEs, diarrhea and neutropenia, are amenable to early recognition and intervention. These events infrequently resulted in treatment discontinuation with management, including dose modifications and supportive care. Many of the more severe TEAEs, such as infections and hematologic abnormalities, are commonly observed in subjects with advanced B-cell malignancies. Adverse events (AEs) of special interest (AESIs), such as diarrhea, colitis, pneumonitis, rash, and transaminase elevations, have been well-described with the use of PI3K- δ inhibitors and immuno-oncology therapies. The most commonly occurring AEs infrequently resulted in treatment discontinuation, representing a manageable safety profile in subjects with advanced hematologic malignancies.

The identified risks for duvelisib treatment are infections, diarrhea/colitis, cutaneous reactions, pneumonitis, transaminase elevations, and neutropenia. Potential risks are hepatotoxicity and reproductive toxicity. Guidance on management of these AEs, including duvelisib dose interruptions and modifications, is provided in Section 6.6 and Section 6.7. Detailed information

about the known and expected risks and reasonably expected AEs of duvelisib may be found in the IB.

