8.3.6. Clinical Laboratory Adverse Events

A clinical laboratory AE is any laboratory value that is deemed clinically significant by the Investigator. The Investigator should decide, based upon the AE criteria and the clinical condition of the subject, whether a change in a laboratory parameter is clinically significant and therefore represents an AE.

The following items may be considered when determining clinical significance:

- Severity of the laboratory abnormality (i.e., greater than Grade 2 in severity)
- Laboratory abnormality requires a medical intervention
- Laboratory abnormality requires a change or suspension of study intervention
- Laboratory abnormality is accompanied by clinical symptoms

Laboratory abnormalities that are not considered clinically significant should not be recorded as AEs and will be captured and reported in the laboratory section of the clinical study report. If a medical intervention occurs, it should be recorded as a treatment with the abnormal laboratory finding as the AE (e.g., anemia with treatment required and blood transfusion recorded as a procedure, hyperglycemia with treatment required and change in insulin dose recorded on concomitant medications).

If, at the end of the treatment phase with the study intervention, there are pathological laboratory values which were not present at Baseline, further clinical or laboratory investigations should be performed until the values return to within reference range or until a plausible explanation (i.e., concomitant disease) is found for the pathological laboratory values.

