**6 APPENDIX****Appendix 1: List of Preferred Terms for Adverse Events of Special Interest**

Grouped Term	Preferred Terms
All infections (excluding Pneumonia and COVID-19 infections)	All preferred terms under SOC = 'Infections Infections and infestations' excluding any preferred term containing the word 'pneumonia' and excluding any preferred terms included in the COVID-19 infections Grouped Term.
Diarrhea	Diarrhoea, Diarrhoea hemorrhagic, Defecation urgency
Colitis	Colitis, Colitis erosive, Enterocolitis, Enterocolitis hemorrhagic, Colitis microscopic, Necrotising colitis, Colitis ulcerative
Pneumonia	Pneumonia, any PT containing the word/string "pneumonia" except for "Pneumonia aspiration", Atypical pneumonia, Atypical mycobacterial pneumonia, Bronchopneumonia, Bronchopulmonary aspergillosis
Pneumonitis	Pneumonitis, Interstitial lung disease, lung infiltration, acute interstitial pneumonitis
Transaminase elevation	Alanine aminotransferase increased, Aspartate aminotransferase increased, Transaminases increased, Hypertransaminasaemia, Hepatic enzyme increased, Acute hepatic failure, Drug-induced liver injury, Hepatic failure, Hepatocellular injury, Hepatotoxicity
Cutaneous reactions	Dermatitis, Dermatitis allergic, Dermatitis bullous, Dermatitis exfoliative, Dermatitis psoriasiform, Drug eruption, Drug reaction with eosinophilia and systemic symptoms, Erythema, Erythema multiforme, Generalised erythema, Exfoliative rash, Rash, Rash generalised, Rash erythematous, Rash follicular, Rash macular, Rash maculo-papular, Rash maculovesicular, Rash papular, Rash papulosquamous, Rash pruritic, Rash pustular, Rash vesicular, Toxic skin eruption, Palmar erythema, Palmoplantar keratoderma, Palmar-plantar erythrodysesthesia syndrome, Perivascular dermatitis, Skin reaction, skin toxicity, Stevens-Johnson syndrome, Toxic epidermal necrolysis
Neutropenia	Neutropenia, Neutrophil count decreased
COVID-19 infections	Asymptomatic COVID-19, Congenital COVID-19, Coronavirus infection, Coronavirus test positive, COVID-19 pneumonia, COVID-19 treatment, Multisystem inflammatory syndrome in children, Post-acute COVID-19 syndrome, SARS-CoV-2 RNA decreased, SARS-CoV-2 RNA fluctuation, SARS-CoV-2 RNA increased, SARS-CoV-2 sepsis, SARS-CoV-2 test false negative, SARS-CoV-2 test positive, SARS-CoV-2 viraemia, Suspected COVID-19, Vaccine derived SARS-CoV-2 infection

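### Protocol 8.2.4 and 8.3.6 use different tests for a clinically significant laboratory finding, so a cytopenia that leads to a hold or treatment can go unrecorded as an AE

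*Protocol*

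**What the plan says.** Protocol 8.2.4 tells the Investigator to review each laboratory report and "record any clinically relevant changes occurring during the study in the AE section of the CRF". It does not define relevance. It then says "Clinically significant abnormal laboratory findings are those which are not associated with the underlying disease", and qualifies this with "unless judged by the Investigator to be more severe than expected for the subject's condition".

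Protocol 8.3.6 makes a laboratory AE any value that the Investigator deems clinically significant, judged by the AE criteria and the subject's clinical condition. Among the items that may be considered is "Laboratory abnormality requires a change or suspension of study intervention". It adds that "Laboratory abnormalities that are not considered clinically significant should not be recorded as AEs". Where a medical intervention is given, however, the intervention is recorded as a treatment and the laboratory finding as the AE; anemia with transfusion is one of its examples.

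Two other protocol sections bear on this. Section 8.3.1 defines an AE without regard to drug relationship, but lets anticipated fluctuations of the disease under study go unreported when there is no clinically significant worsening. Section 8.3.5 provides a separate causality scale.

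On the analysis side, SAP Appendix 1 builds the neutropenia AESI from two reported preferred terms, "Neutropenia, Neutrophil count decreased". SAP 4.11.2 and 4.11.2.1 tabulate TEAEs resulting in dose hold from the same AE records.

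**The concern.** The two sections can give different answers for the same blood count. Under 8.2.4, the presumed cause helps decide whether a finding is significant, and so whether an AE exists at all. Elsewhere the protocol treats cause as an attribute of an AE already recorded. The findings most exposed are cytopenias, because the protocol itself links them to the disease: Section 2.3.1 says "Many of the more severe TEAEs, such as infections and hematologic abnormalities, are commonly observed in subjects with advanced B-cell malignancies".

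The trial asks whether drug holidays keep efficacy with acceptable or improved safety and tolerability. Under Protocol 9.2, safety data feed both the decision to proceed to Stage 2 and the final evaluation of each schedule, and there is no DMC (9.6). If recording depends on which section a site follows, an AE-based neutropenia rate partly reflects site practice. A hold could also appear in the exposure summary with no matching TEAE.

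**Working it through.** No stated power, alpha or sample size depends on this point, so there is no plan figure to reproduce. The check sets the passages side by side and follows single cases through to the outputs.

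**Step 1: the two tests.**

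| Question | Protocol 8.2.4 | Protocol 8.3.6 |
|---|---|---|
| Does association with the disease matter? | Yes: outside the definition, unless judged worse than expected | No such test in this section; it refers to AE criteria, and 8.3.1 has its own disease-fluctuation wording |
| Does a drug hold matter? | Not part of the definition | Listed, but only as something that may be considered |
| Does a medical intervention matter? | Not part of the definition | Yes: the laboratory finding is recorded as the AE |

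**Step 2: a hold.** Table 5 withholds duvelisib when ANC is below 0.5 Gi/L. Suppose the Investigator attributes such a count to lymphoma and thinks it no worse than expected. Under 8.2.4 it is not clinically significant, and 8.3.6 then keeps it out of the AE record. Read on its own, 8.3.6 names the hold as a reason to call the count significant, though it does not compel that.

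**Step 3: an intervention.** Protocol 6.6.2 permits G-CSF and transfusion. A cytopenia treated in this way, with the same attribution, fails the 8.2.4 test but is the AE under 8.3.6. This is the sharper conflict, because 8.3.6 gives a recording instruction here and not merely a list of considerations.

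**Step 4: how easily the exception in 8.2.4 would apply.** Inclusion criterion 5 requires ANC of at least 1.0 and platelets of at least 75 (x 10^9/L). From the lowest counts allowed at entry, reaching a Table 5 hold needs these falls:
- ANC below 0.5: more than (1.0 - 0.5)/1.0 = 50%.
- Platelets below 25: more than (75 - 25)/75 = 67%.
- Platelets below 50, with Grade 2 bleeding: more than (75 - 50)/75 = 33%.

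Falls of this size would often be called worse than expected, and the AE would then be recorded. No rule requires that judgment.

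**Step 5: which outputs are exposed.**
- Exposed: the neutropenia AESI (SAP 4.11.2.1 and Appendix 1) and the tables of TEAEs leading to dose hold (SAP 4.11.2 and 4.11.2.1). SAP 4.11.4 does not close the gap, because it makes the AE follow from the Investigator's call of clinical significance.
- Not exposed: worst CTCAE grade by laboratory test (SAP 4.11.4), the separate Grade 3 or 4 laboratory table and listing (Protocol 9.4.4), and subjects with unplanned holds (SAP 4.11.1). Protocol Appendix 3 requires every test result to be entered in the CRF.

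**The case against.** The strongest reply is that both sections end in Investigator judgment, and the route to a lost AE is narrow. The 8.2.4 definition carries its own exception, and the same section asks for clinically relevant changes to be recorded as AEs. Its last bullet gives a dose modification as an example of what makes a result clinically significant. Section 8.3.6 is permissive about holds and leans on 8.3.1, which has its own allowance for disease fluctuation. A hold for neutropenia needs a count less than half the entry minimum, and Protocol 2.3.1 lists neutropenia as an identified duvelisib risk. An Investigator would have to set all of this aside.

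Most of this stands, and it limits the point to a possibility. It does not remove the conflict. The last bullet of 8.2.4 concerns results from non-protocol tests and their entry in the CRF, not AE recording in general. The instruction on medical intervention in 8.3.6 has no counterpart in the 8.2.4 definition.

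Stronger readings that a reader might infer are not supported:
- **That 8.2.4 leaves out every disease-associated abnormality.** The exception brings some of them back.
- **That neutropenia is undercounted by a calculable amount.** It is tempting to scale down the 34.7% neutropenia rate in Protocol 2.3.1. That figure is a reported TEAE rate across mixed hematologic malignancies, not a true incidence, and the documents give no share of unrecorded events.
- **That anemia holds are lost.** Table 5 has no anemia row, so anemia enters only through intervention.
- **That the transaminase AESI is equally exposed.** The documents give no reason why ALT or AST rises would be attributed to lymphoma.
- **That the imaging rule in 8.1.1, "Any new abnormal findings outside disease measurements should be captured as an AE", is part of the same conflict.** A different threshold for scans is not a contradiction, and tightening it would narrow AE capture.

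**Conclusion.** The point holds as an inconsistency that can lead to under-recording. A cytopenia that leads to a hold or a medical intervention can go unrecorded if three things coincide: the site applies 8.2.4, the Investigator attributes the finding to the disease, and the finding is judged no worse than expected. The neutropenia AESI and the tables of TEAEs leading to hold can then be too low.

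The size cannot be derived from the documents and may be zero. The laboratory and exposure outputs would still show the events, so the likely symptom is disagreement between tables, not complete loss of the signal. Nothing suggests that one arm is affected more than the other: the same wording covers both, and Protocol 9.4.1 plans no formal comparison. The correction is still worth making, because it is cheap and makes AE capture less dependent on site and attribution.

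**What to change.** 1. In Protocol 8.2.4, remove the sentence that ties clinical significance to absence of association with the disease, and refer to 8.3.6 for the definition.
2. In Protocol 8.3.6, state that a laboratory abnormality leading to a hold, reduction or discontinuation of duvelisib, or to a medical intervention, is recorded as an AE whatever its presumed cause, with attribution entered under 8.3.5. The first change alone would not be enough, because the hold criterion in 8.3.6 is only permissive.
3. Make clear that the disease-fluctuation wording in 8.3.1 does not override this rule. Abnormalities with neither consequence remain a matter of judgment under 8.3.6.
4. If conduct is too advanced for a protocol change, add a SAP listing that reconciles Grade 3-4 ANC values and unplanned holds against AE records, so that unmatched events are visible beside the AESI table.

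No dosing or hold rule changes. The cost is a few protocol sentences and a site reminder, or one listing. The downside is a few more laboratory AEs and slightly less favorable neutropenia rates.

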8.3. Adverse Event Management

8.3.1. Definition of an Adverse Event

An AE is defined as any untoward medical occurrence in a subject administered a medicinal product that does not necessarily have a causal relationship with this treatment. An AE can, therefore, be any unfavorable and unintended sign (including an abnormal laboratory finding), symptom, or disease temporally associated with the use of a medicinal (investigational) product, whether or not related to the study (investigational) product. This includes an exacerbation of pre-existing conditions or events, concurrent illnesses, drug interaction, or the significant worsening of the indication under investigation. Anticipated fluctuations of pre-existing conditions, including the disease under study that does not represent a clinically significant exacerbation or worsening, need not be considered AEs.

Symptoms of the disease under study/lack of efficacy/disease progression should not be classified as an AE if they are within the normal day-to-day fluctuation or expected progression of the disease.

It is the responsibility of the Investigator to document all AEs that occur during the study. AEs should be reported on the appropriate CRF.

8.3.2. Definition of a Serious Adverse Event

An SAE is any untoward medical occurrence at any dose (including after the ICF is signed and prior to dosing) that:

- Results in death
- Is life-threatening (subject is at immediate risk of death from the event as it occurred)
- Requires inpatient or prolongation of existing hospitalization
- Results in persistent or significant disability/incapacity
- Results in a congenital anomaly/birth defect

Important medical events that may not result in death, are not immediately life-threatening, or do not require hospitalization may be considered SAEs when, based on appropriate medical judgment, they may jeopardize the subject and may require medical or surgical intervention to prevent one of the outcomes listed in this definition. Examples of such events include allergic bronchospasm requiring intensive treatment in an emergency room or at home, blood dyscrasias or convulsions that do not result in inpatient hospitalization, or the development of drug dependency or drug abuse.

For SAE reporting purposes, hospitalization is defined as inpatient hospital stay. Hospitalizations for elective surgery or other medical procedures that are not related to a TEAE are not considered SAEs. Hospitalization, which in the opinion of the Investigator, is unrelated to the study intervention, and due to purely non-medical circumstances (e.g., respite care, lack of a caretaker at home, lack of transportation home) are also not considered to be SAEs. PD under study (including signs and symptoms of progression) if documented by use of appropriate methods, should not be reported as an SAE unless the outcome of the PD is fatal during the study or within the safety reporting period (see Section 8.3.3, Reporting of Adverse Events and Serious

Adverse Events). If the malignancy has a fatal outcome during the study or within the safety reporting period, then the event should be reported using the term "disease progression" with a Common Terminology Criteria for Adverse Events (CTCAE) severity of Grade 5.

Death should not be reported as an SAE. The primary reason for a subject's death should be reported as an SAE, with death reported as the outcome.

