8.3.3. Reporting of Adverse Events and Serious Adverse Events

The AE reporting period begins from the time that the subject signs the ICF through and including 30 calendar days after the last study intervention dose. All subjects with treatment-related AEs/SAEs should be observed until resolution or stabilization. Any SAE occurring after the reporting period must be promptly reported if a causal relationship to the investigational drug is suspected. If the subject begins a new anticancer therapy, the safety reporting period ends at the time the new treatment is started, however, death must always be reported if it occurs during the AE reporting period irrespective of intervening treatment.

Elective or previously scheduled hospitalizations for pre-existing conditions that have not worsened after initiation of treatment should not be classified as SAEs. For example, an admission for a previously scheduled ventral hernia repair would not be classified as an SAE.

All AEs should be recorded individually unless, in the opinion of the Investigator or designated physician, the AEs constitute components of a recognized condition, disease, or syndrome. In the latter case, the condition, disease, or syndrome should be reported rather than each individual sign or symptom. If a constellation of signs and/or symptoms cannot be medically characterized as a single diagnosis or syndrome at the time of reporting, each individual event should be recorded as an AE or SAE as appropriate on the relevant form(s) (SAE Report Form and/or AE CRF). If a diagnosis is subsequently established, it should be reported as follow-up information becomes available. If a diagnosis is determined after the reporting of the constellation of symptoms, the signs/symptoms should be updated to reflect the diagnosis.

Each AE will be evaluated for duration, severity, seriousness, and causal relationship to the investigational drug. The action taken with study intervention and the outcome must also be recorded.

All SAEs, regardless of relationship to the study intervention, must be reported immediately (within 24 hours of awareness of event by Investigator) to the Sponsor and Contract Research Organization (CRO) pharmacovigilance group. Initial SAE notification should be made by e-mailing or faxing the SAE report form to the e-mail or fax number provided on the SAE report form.

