- TEAEs resulting in dose hold or reduction (all causalities)
- TEAEs resulting in any dose modification (dose hold, dose reduction and/or discontinuation)
- TEAEs occurring during the first 10 weeks of treatment
- Treatment-related TEAEs resulting in discontinuation of study drug
- TEAEs by resolution status (resolved/resolved with sequelae vs. not resolved)
- Grade 3 and or higher TEAEs by resolution status (resolved/resolved with sequelae vs. not resolved)
- Treatment-emergent SAEs by resolution status (resolved/resolved with sequelae vs. not resolved)
- TEAEs resulting in death (all causalities)
- Treatment-related TEAEs resulting in death
- TEAEs reported in  $\geq 20\%$  of all treated subjects by PT (all grades, all causalities)
- Grade 3 or higher treatment-emergent AEs reported in  $\geq 20\%$  of all treated subjects by PT (all causalities)
- Treatment-emergent SAEs reported in  $\geq 2\%$  of all treated subjects by PT (all causalities)
- TEAEs reported in  $\geq 5\%$  of subjects and occurred at  $\geq 2\%$  higher incidence in subjects on Arm 1 (all grades, all causalities)
- Grade 3 or higher TEAEs reported in  $\geq 5\%$  of subjects on either arm (all causalities)

A by-subject listing of the following AE categories will be presented.

- All AEs (TEAEs will be flagged)
- All SAEs (TEAEs will be flagged)
- All SAE reported with the term disease progression
- TEAEs resulting in dose hold
- TEAEs resulting in dose reduction
- TEAEs resulting in discontinuation of study drug
- TEAEs resulting in death (see [Section 4.11.3](#) for full characterization of deaths)
- TEAEs resolved or resolved with sequelae
- TEAEs not resolved

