#### 4.11.3 Deaths, Serious Adverse Events, and Other Significant Adverse Events

A complete tabulation of all deaths occurring on study will be provided, which will include:

- All reported fatal AEs
  - Treatment-emergent fatal AEs by SOC and PT
    - Deaths within 30 days of duvelisib last dose by SOC and PT
    - Deaths > 30 days from duvelisib last dose by SOC and PT
  - Treatment-related treatment-emergent fatal AEs by SOC and PT
    - Deaths within 30 days of duvelisib last dose by SOC and PT
    - Deaths > 30 days from duvelisib last dose by SOC and PT
  - Fatal AEs reported that start > 30 days post duvelisib last dose by SOC and PT

The following listings will also be presented:

- A by-subject listing of all deaths that occurred during the study will be presented and will distinguish between deaths on treatment (through 30 days after last dose of duvelisib), fatal AEs outside the 30 day window, and deaths during survival follow-up
- A by-subject listing of all SAEs
- A by-subject listing of all AEs leading to discontinuation of study treatment
- A by-subject listing of all other significant AEs

Listings will follow the format described for AEs in [Section 4.11.2](#), if appropriate.

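### Fatal lymphoma progression stays in the all-causality serious, Grade 3 or higher, fatal and overview TEAE totals, and the SAP separates it only in a listing

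*Protocol*

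**What the plan says.** **Protocol.** Section 8.3.1 says that symptoms or progression of the disease under study "should not be classified as an AE if they are within the normal day-to-day fluctuation or expected progression of the disease". It also counts a significant worsening of the indication among possible AEs. Section 8.3.2 says that documented progression "should not be reported as an SAE unless the outcome of the PD is fatal during the study or within the safety reporting period", and if the malignancy is fatal, "then the event should be reported using the term 'disease progression' with a Common Terminology Criteria for Adverse Events (CTCAE) severity of Grade 5". The same section asks for the primary reason for a death to be the reported SAE, with death as its outcome. Section 8.3.3 runs the AE reporting period from consent "through and including 30 calendar days after the last study intervention dose".

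**SAP.** Section 4.11.2 defines a TEAE as any AE that emerges or worsens from first dose to 30 days after last dose, without an exception for progression. It plans an overview table and all-causality tables of Grade 3 or higher TEAEs, treatment-emergent SAEs and fatal TEAEs. Progression is handled separately only in a by-subject listing: "All SAE reported with the term disease progression". Section 4.11.3 tabulates fatal AEs by SOC and preferred term, split by relatedness and by timing (for example, "Deaths > 30 days from duvelisib last dose by SOC and PT"), but not by broad cause of death.

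**The concern.** The trial asks two separate questions: whether drug holidays preserve efficacy, and whether they make safety acceptable or better (Protocol 2.1 and 4.2). Fatal progression is an efficacy failure, but under 8.3.2 it enters the safety data as a Grade 5 serious event. A schedule that controlled the lymphoma less well could then show more serious, Grade 3 or higher and fatal events with no added drug toxicity.

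These totals will be used. Protocol 9.2 and SAP 4.13 base the Stage 2 decision and the final evaluation of each schedule on the totality of data, including safety data. There is no data monitoring committee (Protocol 9.6, SAP 4.11.6). The SAP already treats the term as worth isolating, since it lists these events, but it never isolates them in a count.

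**Working it through.** The documents give no figure for this point, so there is none to reproduce. The check traces the reporting rule into the tables and then sizes the effect.

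**1. Which tables a fatal progression enters.** Under Protocol 8.3.2 the event is serious, Grade 5 and fatal. If it falls in the SAP 4.11.2 window it meets the criteria for the serious, Grade 3 or higher and fatal all-causality tables, and for any matching overview category. No SAP rule removes it.

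**2. Which deaths fall in the window.** If the subject dies within 30 days of last dose, the onset cannot be later than the death, so a progression that emerged or worsened after first dose is treatment-emergent however its onset is dated. A death later than that counts only if it is reported at all after the 8.3.3 period and its onset is dated back into the window.

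**3. Size per event.** Input: 51 subjects per arm at full enrolment (Protocol 9.2, SAP 4.13). One event adds at most 1/51 = 1.96, about 2.0 percentage points. For k events the maximum is 100 × k/51. The documents give no rate of fatal progression, so k from 0 to 5 is an assumed range:

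| k | Maximum addition (points) |
|---|---|
| 0 | 0.0 |
| 1 | 2.0 |
| 2 | 3.9 |
| 3 | 5.9 |
| 4 | 7.8 |
| 5 | 9.8 |

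**4. Whether a reader can take it out again.** In one arm, let S be the number of subjects in a total, k the number on the *disease progression* row, and m the number of those k who also have another event of the same kind. The total without progression is S − (k − m), with 0 ≤ m ≤ k.

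- *Fatal table.* One primary reason is reported per death, so m = 0 and the corrected total is exactly S − k. The preferred-term row is enough, assuming the fixed term codes to an identifiable row.
- *Serious and Grade 3 or higher tables.* A subject may have several such events, and the table shows S and k but not m. The corrected total is known only to lie between S − k and S, a width of k/51. For k = 3 that is 3/51 = 5.9 points. The same holds for the matching overview lines.

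**5. Whether a related-only table fills the gap.** SAP 4.11.2 lists treatment-related versions for all TEAEs, maximum grade, Grade 3 or higher, discontinuation and death. It lists none for SAEs, and it does not name the overview categories.

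**The case against.** The strongest reply is that all-causality tables include unrelated events by design, and that the tables meant to show drug toxicity are largely clean. This mostly stands. Treatment-related Grade 3 or higher and fatal tables drop progression judged unrelated, although SAP 4.11.2.1 counts missing causality as related. Progression belongs to no AESI group (SAP Appendix 1). A reader might infer that the safety totals cannot be read as drug safety at all; these other tables show that this goes too far.

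Four further points limit the concern.

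- **Cause of death is not absent.** Because the primary reason for death is the reported term, the fatal table by preferred term already works largely as a cause-of-death table. A rise in the fatal row is therefore visible and correctable.
- **Non-fatal progression is not wholly excluded.** A reader might infer that progression reaches the AE data only when fatal. Protocol 8.3.1 excludes only expected progression and normal fluctuation, and significant worsening can still be an AE.
- **Late deaths are uncertain.** A reader might infer that lymphoma deaths months after treatment will fill the fatal TEAE row. Protocol 8.3.3 ends AE reporting 30 days after last dose and asks for later SAEs only where drug causality is suspected. That inference needs the phrase *during the study* in 8.3.2 to override 8.3.3, and an onset dated at progression. SAP 4.11.3 also has its own row for fatal AEs starting more than 30 days after last dose.
- **Listings allow reconstruction.** The SAE and progression listings let someone rebuild the serious total by hand. That is possible, but it is not a planned result.

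The gap left standing is in the subject-level serious, Grade 3 or higher and overview totals.

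**Conclusion.** The point holds for descriptive, all-causality safety totals. Fatal progression in the treatment-emergent window adds up to 2.0 points per death at 51 per arm, and nothing to the serious or Grade 3 or higher total where the subject already has another such event. The fatal table can be corrected from its own row. The serious, Grade 3 or higher and overview totals cannot be corrected from the planned tables, and for SAEs no treatment-related table is listed to offset this.

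The size rests on full enrolment and on an assumed number of fatal progressions. The documents do not support a claim that the fatal rate would be inflated by any particular multiple. The ORR test is unaffected, and no formal comparison of arms is planned (Protocol 9.4.1). This is a worthwhile reporting change, not a flaw in the primary analysis.

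**What to change.** In SAP 4.11.2, keep the all-cause totals. Add, by arm, the overview, serious, Grade 3 or higher and fatal TEAE totals excluding events reported as *disease progression* under Protocol 8.3.2, and show those events on their own line. In SAP 4.11.3, add a deaths summary by cause: disease progression, adverse event, other. Keep the existing listing.

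The fixed reporting term serves as the programming flag, so no new data, protocol amendment or change in clinical conduct is needed. The cost is SAP wording and a few extra table lines. The drawback is that the split relies on investigators attributing deaths to progression in an open-label trial, which is why the all-cause totals should stay beside it.
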